While the long-term health effects of e-cigarettes are still unclear, studies examining proximal biomarkers of health indicate that e-cig users are exposed to many cardiovascular and pulmonary toxicants, including carcinogens, such as carbonyls, furans, reactive oxygen species, and heavy metals^{6,7}. Early evidence indicates that e-cig users experience adverse health effects, including increased oxidative stress, respiratory and mucosal inflammation, arterial stiffness and altered hemodynamics and platelet activity⁸. Moreover, use of nicotine by youth can adversely affect attention, learning, and memory, as well as lead to increased impulsivity. Taken together these data suggest that sustained e-cig use will likely have notable adverse health effects⁹. Since their introduction in 2015, to our knowledge, no studies have examined the toxicological and physiological effects of NSB device use, nor the impact of nicotine form. Previous research has largely focused on free-base nicotine devices, with only a few focusing on pulmonary and cardiovascular effects.

The youth vaping epidemic in the U.S. is drawing serious concern from parents, schools, health officials and regulators. There is now a wave of support and a need to create effective e-cig policies and regulations to prevent further proliferation of youth e-cig use. One of the most effective policies may be to create a product standard for nicotine to reduce the palatability and abuse liability of e-cigs for youth;

Evaluating E-Cigarette Nicotine Form, Concentration, and Flavors among Youth

however, strong scientific evidence is needed for the FDA to impose such regulations. The proposed project will begin to address this need.

A. Specific Aims

Utilizing a human laboratory design, we will examine the influence of nicotine form and concentration, and e-liquid flavor on youth vaping behavior, nicotine uptake, abuse liability, toxicant exposure, and acute cardiovascular and pulmonary effects. H1a: Nicotine salt (vs. free-base) and menthol flavored e-liquids (vs. tobacco flavored) will result in puffs of longer duration and higher flow rate, and a greater total inhaled aerosol volume, and H1b: demonstrate greater nicotine uptake, abuse liability, and adverse cardiovascular and pulmonary effects. H1c: High concentration, free-base nicotine (vs. salt nicotine) will result in puffs of shorter duration, lower flow rate, less volume, and lower abuse liability.

B. Significance

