This study (Figures 1 and 3) will include Option A consisting of 9 lab visits each approximately 2 hours long, except visit 1, which will last up to 3 hours **OR** Option B consisting of 5 lab visits each containing 2 vaping sessions separated by a 3-hour washout period and lasting approximately 6 hours. Figure 2 illustrates the study e-cig and e-liquid variations. Figure 3 depicts the sequence of the proposed study. We will conduct an experimental study examining how the manipulation of nicotine form (nicotine salt (NSB) vs. free-base (FB)) influences vaping behavior, abuse liability, toxicant exposure and heart and lung health.

Evaluating E-Cigarette Nicotine Form, Concentration, and Flavors among Youth

Figure 1. Vaping Session

Vaping Session	
12 hour nicotine abstinence	
Start of Session:	Surveys Respiratory Measures Cardiovascular Measures Blood Draw (0 min)
STD Puffing (5 min):	Blood Draw (5 min) Surveys
Ad-lib Puffing (30 min): Blood Draw (10 min) Blood Draw (35 min) Surveys	
3-hour washout (Visits 2-5 between vape sessions) (Option B Only)	
3 hrs. post exposure:	Respiratory Measures Cardiovascular Measures (Option B Only)
1 vaping session will occur at each visit for 9 visits (Option A Only)	
1 vaping session will occur at the first visit / 2 vaping sessions will occur at the final 4 visits (Option B Only)	

Figure 2. E-cig and e-liquid for Vaping Sessions

[figure not shown]
[figure not shown]

Figure 3. Study Sequence Option A and Option B

Evaluating E-Cigarette Nicotine Form, Concentration, and Flavors among Youth

ii. Study Procedures

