Utilizing a within-subjects, factorial design, 60 e-cig users (aged 21-25 years) will complete vaping sessions which will include a standardized, 5-minute, 10-puff vaping bout (30 seconds between each puff) followed by 30 minutes of ad libitum vaping. Prior to session one, participants will be asked to bring their own e-cig device and a full tank/pod to the first visit. In session one, participants will use their own e-cig and e-liquid. After visit 1, participants will take home a study e-cig device and 1 weighed pod pre-filled with study e-liquid (the participant was randomized to at the end of visit 1) to practice (20 puffs per day with the study device and until the participant feels comfortable) using the device before visit 2. Practice use with the study e-cig device and pre-filled pod will be verified based on data downloaded (via eScribe) from the device during visit 2. In the subsequent vape sessions, participants will use a study e-cig held at a constant wattage, and pre-filled with e-liquid of different nicotine form (free-base vs. nicotine salt), concentration (low-1% vs. high-5%), and flavoring (tobacco vs. menthol). There is no known commercial pair of nicotine liquids that differ only by nicotine form. For this study, we will prepare 8 e-liquids that differ by nicotine form, nicotine concentration, and flavor, simulating characteristics of popularly used nicotine liquids^{32,39}. E-liquids will be prepared from pure ($\geq 99\%$) S-(-)-nicotine; protonation and dilution of nicotine will be done using USP grade benzoic acid, and glycerol and propylene glycol, respectively. We will submit an Investigational Tobacco Product application to the U.S. FDA regarding the clinical use of the e-liquids. All sessions will be completed over nine visits for schedule Option A and 5 visits for schedule Option B. Study Schedule A consist of 9 separate visits and 9 separate vaping sessions. Study schedule B will consist of five separate visits (each visit will include up to 2 vaping sessions) each separated by a 3-hour washout period to allow nicotine levels to return to baseline. Each visit will be at least 48 hours apart. Participants will be required to report at least 12 hours abstinent from nicotine before each study visit. Participants will be told that their abstinence will be confirmed at the time of visit via blood plasma nicotine analysis. This is a partial bogus pipeline⁴⁰; 3mL venous blood sample will be collected for later analysis.; those with plasma nicotine levels $>3\text{ng/mL}$ at the time of their visit will be replaced post hoc with another participant. We conservatively estimate replacing 10% of participants. Measures of topography, nicotine uptake, abuse liability, subjective effects, and cardiovascular and pulmonary effects will be collected (see Table 1). Exposure to select toxicants, including nicotine and menthol in total particulate matter, and gas phase carbonyls and volatile organic compounds, will also be estimated post hoc using puff playback machine smoking.

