Laboratory Spirometry (SpiroLab)	X	X
Airway Inflammation (NIOX VERO)	X	X
Airway Reactivity (TremoFlo)	X	X
Cardiovascular Measures		
Vascular Reactivity (Vicorder or similar)	X	X
Blood Pressure	X	X
Heart Rate	X	X
Markers of endothelial dependent and independent function		
B-mode ultrasound (Vicorder or similar)	X	X
Arterial stiffness		
Pulse wave velocity and analysis (Vicorder or similar)	X	X

Evaluating E-Cigarette Nicotine Form, Concentration, and Flavors among Youth

E. Statistical Methods

Generalized linear mixed models will be employed to identify associations of nicotine form, nicotine concentration, and flavoring with various outcome measures (e.g., plasma nicotine, spirometry, flow-mediated dilation). Models will include relevant covariates (e.g., gender), a random effect for participant, main effects for nicotine form and concentration, and the interaction between nicotine form and concentration and nicotine form and flavor. Because of multiple measurements tested, we will assume a significance threshold corresponding to one expected false discovery per 100 tests ($p=0.01$).

i. Power Analysis

This study, for each of the main effects and $\alpha = 0.01$, achieves 80% power to detect an effect size of 0.5 standard deviations of the paired differences. For interaction effects, we will estimate 80% power (effect size 0.5 SD) to distinguish between any two of the interaction groups (e.g., free base/low nic, free base/high nic), while correcting for the pairwise tests ($p=0.01/6=0.0017$). Carryover and period effects will also be examined.

ii. Data Analytic Plan

Because product sampling will be randomized using a Latin Square, a fixed effect for session and a random effect for sequence will be included in all analyses.

iii. Missing Data

While we will make every effort to minimize the missing data for this study, missing data can arise due to various reasons. Violation of missing complete at random (MCAR) will be checked by evaluating whether any covariates are associated with missing data. If so, these covariates will be subsequently included and controlled for in the GLMM model. Our primary analysis will use mixed models which assumes Missing At Random (MAR) to deal with the missing data problem. In addition, sensitivity analyses will also be conducted using results from multiple imputation and complete cases strategies.

F. Gender/Minority/Pediatric Inclusion for Research

i. Inclusion of Women and Minorities

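### In Option B, four of the eight test sessions start 3 hours after another study liquid, and the model gives neither carryover nor the t=0 sample a defined role

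*Combined protocol and SAP*

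**What the plan says.** Sections D.i and D.ii offer two schedules, and D.ii.1.b shows that participants choose between them. Option A has one vaping session at each of nine visits. Option B has one at visit 1 and two at each of visits 2 to 5, "each separated by a 3-hour washout period to allow nicotine levels to return to baseline". In both, visits are at least 48 hours apart. D.ii words the 12-hour abstinence requirement and the 3 ng/mL plasma nicotine check per visit. D.ii.2.a has blood drawn at 0, 5, 10 and 35 minutes in every session.

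On order effects, E.ii reads "Because product sampling will be randomized using a Latin Square", and concludes that "a fixed effect for session and a random effect for sequence will be included in all analyses". The last sentence of E.i is "Carryover and period effects will also be examined". Section E also lists a participant effect, the form, concentration and interaction terms, and relevant covariates, with gender as the only example. Plasma nicotine is the first outcome it names. H1b in section A predicts that nicotine salt and menthol liquids will "demonstrate greater nicotine uptake, abuse liability, and adverse cardiovascular and pulmonary effects".

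**The concern.** The plan relies on nicotine being back at baseline after 3 hours, but no stated rule checks this at the second session of the day, because the abstinence rule and the plasma check are tied to the visit.

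If nicotine does remain, the amount depends on which liquid came before. The order terms do not remove that:

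- A session effect shared by both options takes out only the average shift at that position.
- A sequence effect is constant over a participant's eight test sessions.
- Neither follows a shift that exists only in Option B and varies with the previous liquid.

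The t=0 sample would capture such a residue, but section E does not make it a covariate, a base for change or a repeated measure. At stake are the form contrast for nicotine uptake (H1b) and the concentration contrast.

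**Working it through.** The plan gives no figure for carryover, so the only figure of its own to reproduce is the session count.

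**Session count.** Option A: 9 × 1 = 9. Option B: 1 + 4 × 2 = 9. Leaving out the own-device session, each has 8 test sessions. In Option B 4 of 8 follow another study liquid by 3 hours; in Option A 0 of 8 do.

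**Inputs from the documents.** 60 completers, 8 liquids (480 test sessions), a 3-hour gap, a last sample at 35 minutes, and a 0.01 threshold (taken as two-sided).

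**Assumed inputs, none in the documents.** Half-life 1.5, 2 or 2.5 h; session rise 3 ng/mL (1% liquid) and 15 ng/mL (5% liquid); residual SD 4 or 8 ng/mL; 30 of 60 in Option B.

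**Residue.** The fraction left after 3 h is 0.5^(3/h) = 25%, 35% and 44%. At the 35-minute sample (3.583 h) it is 19%, 29% and 37%. With a 2 h half-life, a 15 ng/mL rise leaves 15 × 0.354 = 5.3 ng/mL and a 3 ng/mL rise leaves 1.1. The plan's own per-visit limit is 3 ng/mL.

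**Why the square matters.** In an 8 × 8 cyclic square each liquid has a single same-day predecessor, repeated four times. In a Williams square it has four different ones, once each.

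**Form effect, 35% residue, shift equal to the residue at session start.** The standard error is SD × √(4/480), which is 0.365 at SD 4 and 0.730 at SD 8. Form bias was computed from the design (participant, session, form, concentration, flavor and the two planned interactions) over many random labellings of the liquids. If the bias is treated as normal with standard deviation s across labellings, the false-positive rate is 2 × [1 − Φ(2.576 / √(1 + (s/SE)²))]. For one cyclic square at SD 4: s/SE = 0.414/0.365 = 1.13, and 2.576/√2.286 = 1.70, giving 8.8%. Carryover also inflates the estimated residual variance; allowing for this lowers the rates, as in the last column.

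| Ordering | s (ng/mL) | Formula, SD 4 / SD 8 | With inflated residual variance, SD 4 / SD 8 |
|---|---|---|---|
| One fixed cyclic square | 0.414 | 8.8% / 2.5% | 7-8% / 2.3-2.4% |
| One Williams square | 0.166 | 1.9% / 1.2% | 1.1-1.5% (over the three half-lives) / about 1% |
| Cyclic square relabelled per block of 8 | 0.18 | 2.1% / 1.2% | 1.5% / 1.1% |

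**Sensitivity, one cyclic square.**

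- Half-lives 1.5/2/2.5 h: 3.8/7.2/10.5% at SD 4 and 1.6/2.3/3.0% at SD 8.
- The 35-minute level instead: 2.5/4.8/7.7% and 1.3/1.8/2.4%.
- 25% in Option B: 1.5-2.8% at SD 4. 75% in Option B: 7.9-22.7% at SD 4.
- About 40% of labellings give a form bias under 0.1 ng/mL.

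**Rise from t=0.** The net shift is 0.289 − 0.354 = −0.065 of the previous rise, and the form false-positive rate is about 1.1% at most. With no residue there is no effect.

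**Concentration effect.** No liquid follows itself. Of seven possible predecessors, a 5% liquid has three at 5% and four at 1%; a 1% liquid has four and three. Half the participants and half their sessions are affected, so the mean bias is −(1/7) × (15 − 3) × 0.354 × 1/4 = −0.15 ng/mL, whichever square is used.

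**Does the fix work?** Simulation with one cyclic square, SD 4 and the 35-minute level (1,200 replicates; simulation error about 0.3 points at 1%) gave form false positives of 2.5/4.0/6.3% unadjusted, 1.2/0.9/1.1% with the t=0 covariate, and 1.2/0.9/1.0% using first-of-day sessions only.

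**The case against.** The plan does not overlook order effects. It randomizes by Latin square, fits session and sequence effects, leaves the covariate list open, says carryover will be examined, and collects the t=0 sample that would be needed. On this view only detail is missing. Harm also needs several things together: nicotine left at 3 hours, uptake analysed as a raw level, and an unfavourable square. Uptake paired with a t=0 sample can as naturally be read as a rise, which nearly removes the problem. Figure 1 lists surveys and physiological measures before the t=0 draw, so the true gap may exceed 3 hours.

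Most of this stands and limits the size of the point. It does not close the gap: the carryover sentence names no term, test or consequence, and nothing commits the analysis to t=0.

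A reader might infer three stronger things that the documents do not support:

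- That nicotine does remain at 3 hours. They contain no half-life or plasma data to show it.
- That the form result will be biased, and that enrolling more participants cannot help. That holds for one fixed square. With a freshly labelled square per block of eight, the form-bias SD falls from about 0.41 to 0.18 ng/mL, and the plan does not say how many squares are used.
- That false-positive rates above 10% are to be expected. Those need one cyclic square, raw levels, a small SD and the longer half-life or a high Option B share.

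**Conclusion.** The point holds as a gap in specification with a conditional consequence. Four of eight Option B test sessions start 3 hours after another study liquid, the stated order terms cannot absorb a previous-liquid shift confined to Option B, and t=0 has no role in the model.

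If nicotine remains and raw levels are analysed, the form false-positive rate could lie anywhere from close to its nominal 1% to about 7-8% in the central illustration, depending mainly on the square and the residual SD. A small mean concentration bias, about −0.15 ng/mL against a standard error of 0.37 to 0.73, remains whichever square is used. All these sizes rest on assumed half-life, rises, SD and Option B share. Puff topography, spirometry and vascular outcomes were not sized. The change is worth making because it is nearly free and settles the choice before results are seen.

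**What to change.** In E.ii:

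1. For plasma nicotine, add that session's own t=0 value as a covariate. The blood is already drawn, and the variance of the form effect rises by about 0-1% if there is no carryover. Do the same for other outcomes only where a start-of-session value is collected.
2. Add a sensitivity analysis restricted to the first session of each day. With half in Option B it keeps 480 − 30 × 4 = 360 sessions at about 1.4 times the variance. With 75% in Option B it keeps 480 − 45 × 4 = 300 at 1.8-1.9 times. It should support the main analysis, not replace it.

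Optional: state the type and number of squares and, for participants not yet randomized, use a carryover-balanced (Williams) square within each option. This reduces the problem but does not remove it, because only 32 of the 56 ordered pairs fall on the same day. Second-of-day and previous-concentration terms are best kept as an exploratory check where estimable. With half in Option B and a cyclic square they raise the variance for concentration by 7.5% on average and 2.4 times at worst (6.2 times at worst with 75% in Option B).

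Separately, the sponsor should reconcile three passages: 12-hour abstinence before each visit (D.ii), 12-hour abstinence nine times (G.ii, although Option B has five visits), and the 3-hour same-day washout.

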Nevertheless, all participants will be screened for general medical precautions (pregnancy, cardiovascular disease) and monitored for adverse events during the study period. Study personnel will assess for adverse events via self-report at all follow-up visits. Any serious adverse events will be reported to the study's DSMB, and then to the OSU IRB and to the NIH. We will withdraw participants who have a serious adverse event, or become pregnant, begin to breastfeed, or have a cardiovascular or pulmonary event during the study. The most likely adverse (potential for nicotine overdose) event is anticipated to be rare (<5% in our team's previous studies) and mild (nausea, headache, disrupted sleep), and will be handled quickly (i.e., advice to participant to reduce or stop e-cig use). Lab studies of toxin exposure suggest that e-cigs incur no greater risk to health than do conventional cigarettes. Indeed, e-cigarettes generally show lower levels of harmful and potentially harmful constituents. To date, e-cigarette studies discussing adverse events report mild and tolerable side effects that generally resolved completely over time with continued use; the most predominant of which were mouth/throat irritation, cough, and headache. In four randomized clinical trials, no serious adverse events were reported, and the e-cigarette group and the nicotine patch group had comparable levels of adverse events in two studies. The most common were mouth irritation, throat irritation, dry cough and headache. Following the completion of the study, we will encourage all participants to quit their use of e-cigarettes.

2. Loss of Confidentiality and Privacy:

Risks

There is a risk of breach of confidentiality or a loss of privacy associated with taking part in the study.

Protections

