The data and safety monitoring plan will involve the continuous evaluation of safety, data quality and data timeliness. Investigators will conduct continuous review of data and patient safety at their regular Disease Group meetings (at least monthly). The PI of the trial will review toxicities and responses of the trial where applicable at these disease center meetings and determine if the risk/benefit ratio of the trial changes. Frequency and severity of adverse events will be reviewed by the PI and compared to what is known about the agent/device from other sources; including published literature, scientific meetings and discussions with the sponsors, to determine if the trial should be terminated before completion. Serious adverse events and responses will also be reviewed by the OSUCCC Data and Safety Monitoring Committee (DSMC). The PI will also submit a progress report (biannually for Phase II and quarterly for Phase I) that will be reviewed by the committee per the IRB of record as per the policies of the IRB. All Serious Adverse Events are to be submitted to the DSMC for their review. Submissions are made via OnCore.

Adverse Events

Adverse events will be assessed by study staff at each visit via participant self-report and managed immediately. All adverse events will be reported to the OSU IRB. We will monitor for risk of smoking/vaping by screening participants for general medical precautions (pregnancy, cardiovascular disease). Any adverse events, breaks of confidentiality, or any other data or safety issues that arise will be discussed immediately between study personnel and [name]. [name] will be responsible for completing an Adverse Events Form should an event occur. [name] will report Serious Adverse

Evaluating E-Cigarette Nicotine Form, Concentration, and Flavors among Youth

Events to the OSU IRB within 24 hours of having received notice of the event. [name] will gather any information needed to investigate the event and to determine subsequent action. Any subsequent action will be documented and reported to the OSU IRB and the Program Officer at NIH. Adverse event reports will be reviewed annually with the OSU IRB to ensure participant safety.

Collection of Adverse Events

The collection of adverse events will be on a self-report basis and logged within an electronic data capture system (REDCap) or collected using standardized paper forms and will only be identified with the study ID of the participant.

I. Addendum

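### Adverse events are compared only with outside sources: no comparison by assigned liquid and no denominator is specified, so an excess on the 5% liquids relative to the 1% liquids need not be seen

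*Combined protocol and SAP*

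**What the plan says.** Section H.ii (Data and Safety Monitoring Board) has the PI review adverse events at meetings held at least monthly. The stated standard is external: "Frequency and severity of adverse events will be reviewed by the PI and compared to what is known about the agent/device from other sources". The stated purpose is "to determine if the trial should be terminated before completion". No split by liquid, denominator or threshold is given.

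Under Adverse Events and Collection of Adverse Events in Section H, events are self-reported at each visit, and each record "will only be identified with the study ID of the participant". All events go to the IRB, and serious ones also go to the DSMC.

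Section G.ii.1 describes the most likely event, potential nicotine overdose, as "anticipated to be rare (<5% in our team's previous studies) and mild (nausea, headache, disrupted sleep". It does not say whether that percentage counts participants or sessions.

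Section E will use mixed models to "identify associations of nicotine form, nicotine concentration, and flavoring with various outcome measures (e.g., plasma nicotine, spirometry, flow-mediated dilation". Adverse events are not named there and do not appear in Table 1.

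Section D.ii sets out the exposure. It consists of the participant's own device at visit 1, a take-home practice pod before visit 2, and then eight liquids crossing form, concentration (1% or 5%) and flavor. Figure 1 shows one session per visit under Option A and two sessions at each of the last four visits under Option B.

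**The concern.** The external comparison treats the agent or device as a single thing, whereas every completer uses eight liquids with a five-fold range of nicotine concentration. The harm the plan itself expects is nicotine-related, so dependence on concentration is plausible. The within-subjects design supplies a randomized internal comparator, and the plan does not commit to using it for adverse events. For nicotine form, Section D.ii states that no known commercial pair of liquids differs in form alone, so outside data on marketed products are a poor substitute.

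At stake is whether a difference in tolerability between concentrations or forms would be seen, either during the monitoring that informs early termination or in the final report. The abstract and Section G.iii present the study as evidence for regulating nicotine in these products, so tolerability by concentration and form is directly relevant.

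**Working it through.** **Inputs.** 60 completers and 8 study liquids, of which 4 are at 5% and 4 at 1% (Section D.ii). Anticipated rate under 5%, unit not stated (Section G.ii.1). That rate is quoted from the team's previous studies without inputs, so it cannot be reproduced, and Section H does not make it a threshold. It is used here only as the plan's own idea of a rate that would look as expected. At most one event per session is counted, and only completers are counted.

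**Per-session reading.**
- Study sessions: 60 × 8 = 480, with 240 at each concentration.
- Under 5%: 0.05 × 480 = 24, so at most 23 events; 23/480 = 4.8%.
- All on the 5% liquids: 23/240 = 9.6%, against 0/240 = 0% on the 1% liquids. Fisher's exact test, treating sessions as independent, gives p of about 1 × 10⁻⁷. A very clear internal difference is thus compatible with an unremarkable overall rate.
- Adding the own-device session: 60 × 9 = 540; 0.05 × 540 = 27, so at most 26 events; 26/240 = 10.8%.
- With some events on the 1% liquids (assumed rates): an overall 5% means (p₁ + p₅)/2 = 5%, so p₅ = 10% − p₁. Rates of 1%, 2% and 3% on the 1% liquids allow 9%, 8% and 7% on the 5% liquids.
- At assumed true rates of 1% and 8% (overall 4.5%), the observed overall rate stays below 5% with probability 0.67.

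**Per-participant reading.**
- 0.05 × 60 = 3, so under 5% means at most 2 participants.
- Everyone uses every liquid, so no liquid can affect more than 2/60 = 3.3% of participants. Only a relative excess such as 2 against 0 could go unseen, and it would be inconclusive anyway (2/240 against 0/240: Fisher p = 0.50).

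**Attribution.** Under Option A there is one liquid per visit, so study ID with visit and onset dates should identify the liquid. Under Option B each of visits 2 to 5 has two liquids separated by a 3-hour washout, and events are assessed per visit. Without an onset time or session code, the record described cannot say which liquid was in use. Some expected events, such as disrupted sleep, would follow both sessions and may not be separable at all.

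**What a table by liquid could show.**
- Each liquid has 60 sessions. At a true 5% rate, the chance of at least one event is 1 − 0.95⁶⁰ = 95.4%. With 0/60, the one-sided 95% upper limit is 1 − 0.05^(1/60) = 4.9%.
- Comparing 240 with 240 sessions at two-sided 0.01 (sessions treated as independent, rates assumed), power is 87% for 1% v 8%, 53% for 2% v 7%, and 37% for 2% v 6%. A formal test would find only large excesses.

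**The case against.** The strongest case on the other side is that this is silence rather than a wrong method.

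- Section H.ii does not say that frequency is pooled over liquids, nothing forbids a split, and no blinding of the PI is described. This stands: a reader might infer that the plan would report one pooled rate, but the text does not say so. Section E's outcome list is also only illustrative.
- The study-ID sentence reads mainly as a confidentiality statement. A reader might take it to rule out a liquid or session code. It does not, since it says nothing about the form's other fields.
- Other safeguards exist: review at least monthly, immediate discussion of every event, IRB reporting of all events and DSMC review of serious ones. Some 23 events handled one by one could well prompt a look by liquid. That is true, but none of these steps specifies such a comparison, and the expected mild events would not normally reach the DSMC.
- Plasma nicotine is modelled by form and concentration, and heart rate and blood pressure are measured at study visits, so nicotine exposure by liquid will be visible. This also stands, but exposure is not tolerability.
- A reader might name free-base liquid as the likely site of excess overdose. The plan's hypotheses point the other way: H1b expects greater uptake with salt, and H1c expects shorter puffs and less volume with high-concentration free-base. Section B.2 does call unprotonated nicotine more bioavailable, so the direction is open. That is a reason to tabulate by form, not to predict an excess on free-base.

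**Conclusion.** The concern holds in limited form. The only yardstick stated for adverse event frequency and severity is external, no denominator is given, and no comparison by assigned liquid is planned in a design that provides one. An excess on the 5% liquids relative to the 1% liquids need not be seen.

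Its size depends on a unit the plan leaves open. Read per session, a rate of 4.8% could conceal 9.6% against 0%. Read per participant, little can be hidden. The session figures are a limiting case and the liquid-specific rates are assumptions, because the documents give none. The Option B attribution gap does not depend on those rates.

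The documents do not support going further and saying that the trial will issue a wrong safety message. This is a worthwhile, inexpensive improvement to recording and reporting.

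**What to change.** In Section H, under Adverse Events and Collection of Adverse Events:

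- Record for each event the onset date and time, and the liquid and session in use (own device, practice pod or named test liquid). Mark Option B events that cannot be assigned to one liquid, and count them separately by visit.
- State the denominators, both participants and sessions.
- Report counts with exact intervals by liquid, concentration and form, as a descriptive within-person comparison beside the external one. For a single liquid each participant contributes one session. For concentration and form each contributes four, so base those intervals on participants with at least one event.
- Label any formal within-person test exploratory, and limit it to events attributable to one liquid.

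The cost is a few fields on the existing form and one table, with no extra visits or procedures. The downside is that sparse events give wide intervals and a formal test would detect only large excesses, so the absence of a visible difference must not be read as equal tolerability.
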